If a participant experiences somatic or psychological symptoms that interfere with his/her ability to participate then he/she will be discharged from the study. The most frequent symptom is pain over the area of stimulation which could interfere with participation in the study. DLPFC stimulation has rarely been associated with mania. The investigators will monitor participants for changes in mood and may discharge a participant at any time if they believe that it is in the best interest of the participant.

iv. Participant Monitoring

The iTBS monitoring questionnaire, the modified version of the PANAS (see Appendix 1 & 15), and staff observation and interactions with participants will be assessed daily. A NIDA-IRP physician or physician's assistant knowledgeable about iTBS will be immediately available in the building whenever iTBS is administered and will be available by telephone or pager 24 hours a day for consultation or in the event of a medical emergency. If immediate medical intervention is required, the participant will be referred to an appropriate medical facility. Information on all adverse events will be cumulated and reported to the NIDA IRB with each continuing review application. Unexpected or serious adverse events (defined in accordance with NIH and NIDA IRP policy) will be promptly reported to the NIDA Clinical Director and IRB in accordance with NIH and NIDA IRP policy.

Seizure monitoring procedures: Participants will be monitored throughout each iTBS session for signs of seizures such as involuntary muscle movements or loss of consciousness. In the event of a seizure, staff will have immediate access to life support equipment and anti-seizure drugs. In the event of a seizure, the procedure outlined below¹²⁹ will be followed:

1. Protect patient's head and limbs from injury.
2. Ensure an adequate airway.
3. Call 911 to have the patient transferred to Johns Hopkins emergency room.
4. Observe Patient for:
 - a. Initial movements/ sensations.
 - b. Progression of movements.
 - i. Change in respiratory status
 - ii. Skin color
 - iii. Incontinence
 - iv. Level of consciousness
 - v. Ability to communicate
 - vi. Level of orientation
 - vii. Duration of seizure activity

If after two minutes, the seizure has not resolved, administer:
midazolam IM, 10 mg that is contained in a lock box in the TMS suite.

5. Provide supportive care after the seizure resolves.
6. Orient patient to time and place.

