If a participant experiences somatic or psychological symptoms that interfere with his/her ability to participate then he/she will be discharged from the study. The most frequent symptom is pain over the area of stimulation which could interfere with participation in the study. DLPFC stimulation has rarely been associated with mania. The investigators will monitor participants for changes in mood and may discharge a participant at any time if they believe that it is in the best interest of the participant. Participants who fail to tolerate iTBS at 100% of RMT during their toleration session will be discharged from the study. Those with RMT over 83% of MSO will be discharged as the recruitment curves require administering pulses up to 120% RMT, which is only possible if RMT is 83% or less.

7. Participant Monitoring

The NIBS monitoring questionnaire (Appendix 1), Trails A and B (Appendix 22), and staff observation and interactions with participants will be assessed daily. A NIDA-IRP physician or Physician's Assistant knowledgeable about iTBS will be immediately available in the building whenever iTBS is administered and will be available by telephone or pager 24 hours a day for consultation or in the event of a medical emergency. If immediate medical intervention is required, the participant will be referred to an appropriate medical facility. Information on all adverse events will be cumulated and reported to the NIH IRB with each continuing review application. Unexpected or serious adverse events (defined in accordance with NIH and NIDA IRP policy) will be promptly reported to the NIDA Clinical Director and IRB in accordance with NIH and NIDA IRP policy (see DSMP below).

Seizure monitoring procedures: Participants will be monitored throughout each iTBS session for signs of seizures such as involuntary muscle movements or loss of consciousness. In the event of a seizure, staff will have immediate access to life support equipment and anti-seizure drugs. In the event of a seizure, the procedure outlined below¹²⁹ will be followed:

1. Protect patient's head and limbs from injury.
2. Ensure an adequate airway.
3. Call 911 to have the patient transferred to Johns Hopkins emergency room, if the seizure requires medication intervention to resolve or is otherwise clinically indicated.
4. Observe Patient for:
 - a. Initial movements/ sensations.
 - b. Progression of movements.
 1. Change in respiratory status
 2. Skin color
 3. Incontinence

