Endorsing suicidality on the MADRS is an example of a red flag. If a participant endorses this state while the MADRS is administered, a flag is generated, and usually addressed immediately by the clinician administering the MADRS. If a participant reports suicidal thoughts, the CDW Critical Item Alert System will be initiated following the NIDA SOP. Participants may also endorse acute states of depression or mania while participating in this study. Sleep patterns will be tracked to assess potential sleep deprivation. Significant sleep deprivation, or lack of sleep, may have a clinical impact on participants. If this occurs, the LAI will initiate the intervention protocol. This intervention may include referral and/or discharge from the study if clinically significant.

i. Primary Safety Endpoints and Associated Stop Rules

Three outcomes will be monitored throughout the study as safety endpoints associated with a stop rule. As described below, we will track iTBS-induced seizures,

neurocognitive function, and clinically significant adverse events requiring outside evaluation. Chi-square tests will be calculated to test frequency differences between groups (active iTBS vs sham iTBS) for each of these endpoint measures. Each **stop rule** is described in detail below.

1. **Number of iTBS-induced seizures:** more than 1 iTBS-induced seizure resulting in hospitalization within any 10 consecutive participants who receive iTBS will result in a protocol hold until further evaluation by the PI, FDA, and DSMB. The Blind will be broken for any participant with an iTBS-induced seizure. We will also consult [name], M.D., Ph.D., Director, Neuromodulation Program within the Division of Epilepsy and Clinical Neurophysiology, Department of Neurology, Boston's Children's Hospital and Associate Professor of Neurology at Harvard Medical School. [name] is a member of our DSMB and possesses the necessary clinical expertise to evaluate the proposed safety endpoints. No new iTBS sessions will be administered to any participant once this stop rule is enacted until evaluation of the events is concluded and it is deemed appropriate to proceed. However, participants who have completed their iTBS treatments may be scheduled for Contingency Management (CM), MRI scan, or follow-up visits.

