2. **Cognitive performance on Trails B:** Neurocognitive function will be assessed with Trails A and B before and after each iTBS day. Although Trails A and B are usually administered in sequence, **only Trails B** will be evaluated in relation to this stop rule. A completion time for Trails B greater than 90 seconds¹⁶⁹ is considered abnormally long. Therefore, **if a participant requires more than 90 seconds to complete Trails B after iTBS, the following steps will be taken:**
 - a. The participant will rest and be observed for 60 minutes after completion of post-iTBS Trails B.
 - b. Trails A and B will be administered again after the 60 minute timeout period.

- c. A score to complete Trails B a second time greater than 90 seconds will call for the MAI (or covering clinician) to evaluate the participant.
- d. If the MAI (or covering clinician) deems outside evaluation or treatment is necessary, the participant will be discharged from the study and appropriate steps will be taken to seek an outside evaluation/intervention (e.g., an ER visit). The Blind will be broken for this participant at this time.

If more than 1 neurocognitive event identified with Trails B is seen within any 10 consecutive participants, the protocol will be put on hold until further evaluation by the PI, FDA, and DSMB. As above, [name] will be consulted for his evaluation of the stop rule; CM, MRI scan, and follow up visits, may continue but iTBS will not be administered until the hold is resolved.

- 3. **Clinically significant adverse events (i.e. adverse events that require referral for further evaluation) likely related to iTBS.** For example, a mild headache after iTBS that resolves spontaneously or with over-the-counter medication will not be considered clinically significant. A severe headache that starts during or shortly after iTBS and fails to resolve with time and/or OTC intervention would prompt referral to an Emergency Department and will be considered clinically significant.
 - a. If more than 1 clinically significant adverse event related to iTBS administration and having similar clinical features is seen within any 10 consecutive participants, the protocol will be put on hold until further evaluation by the PI, FDA, and DSMB. As above, [name] will be consulted for his evaluation of the stop rule; CM, MRI scan, and follow up visits, may continue but iTBS will not be administered until the hold is resolved.

ii. Clinical Efficacy Cocaine Use Endpoint

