4. If either the primary or secondary stop rules are triggered (described below).

C. Stop or Change Rules

i. Primary Safety Endpoints and Associated Stop Rules

Three outcomes will be monitored throughout the study as safety endpoints associated with a stop rule. As described below, we will track iTBS-induced seizures, neurocognitive function, and clinically significant adverse events requiring outside evaluation. Chi-square tests will be calculated to test frequency differences between groups (active iTBS vs sham iTBS) for each of these endpoint measures. Each **stop rule** is described in detail below.

1. **Number of iTBS-induced seizures:** more than 1 iTBS-induced seizure resulting in hospitalization within any 10 consecutive participants who receive iTBS will result in a protocol hold until further evaluation by the PI, FDA, and DSMB. The Blind will be broken for any participant with an iTBS-induced seizure. We will also consult [name], M.D., Ph.D., Director, Neuromodulation Program within the Division of Epilepsy and Clinical Neurophysiology, Department of Neurology, Boston's Children's Hospital and Associate Professor of Neurology at Harvard Medical School. [name] is a member of our DSMB and possesses the necessary clinical expertise to evaluate the proposed safety endpoints. No new iTBS sessions will be administered to any participant once this stop rule is enacted until evaluation of the events is concluded and it is deemed appropriate to proceed. However, participants who have completed their iTBS treatments may be scheduled for Contingency Management (CM), MRI scan, or follow-up visits.
2. **Cognitive performance on Trails B:** Neurocognitive function will be assessed with Trails A and B before and after each iTBS day. Although Trails A and B are usually administered in sequence, **only Trails B** will be evaluated in relation to this stop rule. A completion time for Trails B greater than 90 seconds¹⁶⁹ is considered abnormally long. Therefore, **if a participant**

requires more than 90 seconds to complete Trails B after iTBS, the following steps will be taken:

1. The participant will rest and be observed for 60 minutes after completion of post-iTBS Trails B.
2. Trails A and B will be administered again after the 60 minute timeout period.
3. A score to complete Trails B a second time greater than 90 seconds will call for the MAI (or covering clinician) to evaluate the participant.

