1. so requests, or withdraws consent.
2. is an HC participant whom requires study visits to be rescheduled more than twice for positive urine triage.
3. develops an exclusionary medical condition or medical problem, for which, in the MAI's judgment, it is in the participant's best interest to be withdrawn from the study.
4. becomes or is found to be pregnant.
5. Participants withdrawn from the study for any medical concerns will be referred for appropriate medical follow-up.

X. DATA/RECORDS MANAGEMENT

Medical and questionnaire data will be gathered in the CDW, a secure database on a closed network. Access to records in the CDW is protected by a system of password-protected accounts and monitored by the Clinical Director (CD).

Data (physiological, behavioral) obtained during experimental sessions is stored on password protected, network drives, which have limited access. Data stored on these drives are identified by study number, participant code number, and/or task. Some files may also include age, race and gender. No personal identifiers are stored with the data. Imaging data is stored on a password-protected LINUX computer with limited access. Data on this server is identified by participant number only with no other identifying information. These data are backed up nightly to a second secure server.

XI. COMPENSATION

All participants:

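### The seizure stop rule counts only seizures that lead to hospitalization, so two iTBS-induced seizures managed on site without referral trigger neither an automatic hold nor an ad hoc DSMB review

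*Combined protocol and SAP*

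**What the plan says.** Section IV.C.i introduces the first primary safety endpoint without a qualifier: "we will track iTBS-induced seizures". The blind is to be broken for any participant who has one. The hold is narrower: "more than 1 iTBS-induced seizure resulting in hospitalization within any 10 consecutive participants who receive iTBS will result in a protocol hold". Section IX.C.i repeats the rule with the same restriction.

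The seizure procedures for the Expanded Feasibility Study (III.G.iii.7 and IV.C) call for an ambulance to the emergency room only "if the seizure requires medication intervention to resolve or is otherwise clinically indicated". Midazolam is given if the seizure has not resolved after two minutes. The completed Pilot (II.E.iv) had the same step, "Call 911 to have the patient transferred to Johns Hopkins emergency room", with no condition attached.

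Three other provisions bear on the point:

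- Stop rule 3 holds the protocol for more than one iTBS-related event with similar features in 10 consecutive participants, but counts only "adverse events that require referral for further evaluation".
- Section IX.B schedules DSMB review yearly in this phase and, in addition, "If either the primary or secondary stop rules are triggered".
- Section IX.G withdraws a participant who "develops an exclusionary medical condition or medical problem, for which" the medical investigator judges withdrawal to be in that person's best interest, and refers anyone withdrawn for a medical concern for follow-up.

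**The concern.** The hold depends on where a participant was managed after the seizure, not on whether iTBS caused one. The kind of seizure the rule leaves out is the kind the protocol leads one to expect: section V.B.ii reports that rTMS-induced seizures so far were short-lived and ended on their own. A seizure that stops within two minutes calls for no midazolam and, unless a clinician sees another reason, no transfer.

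The restriction also leaves rule 1 with little work to do. Two hospitalized iTBS-induced seizures would ordinarily be referred events with similar features, so rule 3 would already hold the protocol at the same threshold. The dedicated seizure rule adds protection mainly if it reaches seizures that were not referred. As written, two severe headaches sent to an emergency department stop stimulation for everyone, while two seizures managed in the TMS suite do not.

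**Working it through.** The plan gives no operating characteristic for this rule, so there is no figure of its own to reproduce. The check has three parts.

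**1. Trace of the scenario.** Two iTBS-induced seizures occur within 10 consecutive participants. Both resolve on site, and neither participant is hospitalized or referred.

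| Provision | Counts | Result |
|---|---|---|
| Rule 1 (hospitalized seizures) | 0 of 2 | no hold |
| Rule 2 (Trails B time) | not triggered by a seizure as such | no hold |
| Rule 3 (events needing referral) | 0 of 2 | no hold |
| Cocaine-use rule (binge spending) | not triggered by a seizure | no hold |
| Ad hoc DSMB review (IX.B) | needs a triggered rule | not started; next scheduled review is the annual one |
| Unblinding (IV.C.i), withdrawal (IX.G) | individual case | iTBS continues for others |

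**2. Chance of a needless hold if every seizure counted.** Inputs:

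- Table 2 (III.G.iv): 1 seizure in 16,952 iTBS sessions, so r = 1/16,952 = 0.059 per 1,000, which agrees with the printed .06.
- Active cocaine-dependent participants: 10 days × 3 sessions = 30 sessions each, 45 planned.
- Healthy controls: 3 active sessions each, 45 planned.

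Formula (Poisson): P(≥2) = 1 − exp(−L)(1 + L), where L = sessions × rate.

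| Setting | L | P(≥2) |
|---|---|---|
| 10 active participants, 300 sessions, rate r | 300/16,952 = 0.0177 | 0.000155 |
| Same, exact 95% upper limit (5.57 events per 16,952) | 300 × 5.57/16,952 = 0.0986 | 0.0046 |
| Same, 10 times r | 0.177 | 0.0139 |
| All active treatment-day sessions, 45 × 30 + 45 × 3 = 1,485, rate r | 1,485/16,952 = 0.0876 | 0.0036 |
| Same 1,485 sessions, upper limit | 1,485 × 5.57/16,952 = 0.488 | 0.087 |

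The last two rows are the chance of two or more seizures anywhere in the study. They therefore exceed the chance of two within some run of 10 participants. Ten active cocaine-dependent participants in a row is also the heaviest exposure, because real runs will include sham participants and controls.

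A binomial version, which counts participants instead of seizures, gives a per-participant risk of 1 − (1 − 1/16,952)^30 = 0.00177 and P(≥2 of 10) = 0.00014. The conclusion is the same.

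**3. Sensitivity lost when the true risk is high.** Let p be the per-participant seizure risk and h the share of seizures hospitalized. Both are assumptions, because the documents give neither for this population. P(hold in one block of 10) = P(Binomial(10, p × h) ≥ 2):

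| p | all counted (h = 1) | h = 0.5 | h = 0.25 | h = 0 |
|---|---|---|---|---|
| 5% | 0.086 | 0.025 | 0.007 | 0 |
| 10% | 0.264 | 0.086 | 0.025 | 0 |
| 20% | 0.624 | 0.264 | 0.086 | 0 |

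These values show how the qualifier weakens rule 1. They are not forecasts, and they ignore rule 3, which would recover the seizures that were referred without admission.

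**The case against.** The strongest reply is that other provisions nearly close the gap. A history of seizure is exclusionary (III.F.iii), so an iTBS-induced seizure plausibly leads to withdrawal under IX.G. Referral after a medical withdrawal is mandatory, and a referred event could count under rule 3, which has the same threshold and the same consequence. Seizures that need medication go to the emergency room and would probably count there too. One DSMB member may be consulted after any seizure (the text can be read that way), the board has access to adverse-event information (IX.F), and serious events are promptly reported. On this view, what remains is a brief, unmedicated seizure with no withdrawal and no referral, occurring twice.

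That narrows the gap but does not close it. Withdrawal under IX.G rests on the medical investigator's judgment, and follow-up after withdrawal is not the same wording as the further evaluation that rule 3 requires. Consultation, reporting and board access leave a hold to discretion, which a stop rule is meant to remove.

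A second reply is that the Poisson figures omit syncope mistaken for seizure, an ambiguity that section V.B.ii acknowledges. It is true that such events are not in the calculation. But the plan must already decide that an event is an iTBS-induced seizure in order to break the blind, and admission to hospital does not settle the cause.

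Two smaller points stand. The session count leaves out the orientation exposure; assuming one extra session each, 310 sessions give L = 0.0183 and P = 0.000165. The Pilot's unconditional ambulance call governs a finished phase and serves only as a contrast.

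**Conclusion.** The concern holds, limited to seizures that are neither hospitalized nor referred. For that pattern no provision automatically suspends iTBS for other participants or convenes the DSMB before its annual review. How often the pattern would arise cannot be computed from the documents; at the Table 2 rate it would be very rare. The case for change rests on what two seizures in 10 participants would mean. Their probability is about 0.00015 at the Table 2 rate and about 0.005 at its 95% upper limit, so their occurrence would point to a rate above that background regardless of disposition. This assumes that the survey rate carries over to cocaine users and that sessions are independent. It is a design choice that should be fixed, not an arithmetic error.

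**What to change.** Delete the three-word hospitalization qualifier from rule 1 in IV.C.i and IX.C.i. The rule would then place the protocol on hold, pending evaluation by the PI, FDA and DSMB, after more than one iTBS-induced seizure of any disposition within any 10 consecutive participants who receive iTBS. This matches the endpoint as introduced, and the ad hoc review in IX.B follows without further change. The transfer procedures in III.G.iii.7 and IV.C can stay as they are.

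The cost is an amendment to two duplicated sections, with IRB, FDA and DSMB notification. The downside is a possible hold for two seizures that would not have counted before, with the small probabilities given above, plus any events wrongly classified as iTBS-induced seizures, which those probabilities do not cover.

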On iTBS days, participants will complete several questionnaires in addition to the iTBS treatments. During iTBS, participants will view cocaine cues (i.e., pictures; Appendix 25) in an attempt to control affective state across participants while also potentially eliciting activation in networks specifically related to cocaine use and substance abuse in general.

Pre-iTBS. Participants will complete a questionnaire about possible side-effects since the last iTBS session (the NIBS monitoring questionnaire) and a questionnaire about their affect (the modified version of the PANAS; see Appendix 1 & 15). Participants will also complete Trails A and B (Appendix 22) prior to and following iTBS administration each day. These assessments will also be collected at baseline prior to any TMS or iTBS administration to assess a true baseline measure for each participant. Also, measures of mania (Young Mania Rating Scale [YMRS]; Appendix 23), suicidality (Columbia-Suicide Severity Rating Scale: Baseline [C-SSRS]; Appendix 24) and depression (MADRS¹¹²; Appendix 14) will be collected prior to the first iTBS session in CD.

iTBS Session. Resting motor threshold will be determined daily, as described below. Recruitment curves will be measured during orientation (HC and CD), and in the CD group, before the first iTBS administration on iTBS day 1, after the last iTBS administration on iTBS day 10, and each of the follow-up visits with an MRI scan. Approximately 1 hour.

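### The between-arm safety comparison of Trails B makes no use of the pre-iTBS times the trial collects, so it is insensitive to modest slowing and cannot separate prior slowness from slowing by iTBS

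*Combined protocol and SAP*

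**What the plan says.** **What is collected.** The iTBS Sessions section (III.G.i.4, Pre-iTBS) states: "Participants will also complete Trails A and B (Appendix 22) prior to and following iTBS administration each day". It adds: "These assessments will also be collected at baseline prior to any TMS or iTBS administration to assess a true baseline measure for each participant". The stop-rule section repeats the daily design: "Neurocognitive function will be assessed with Trails A and B before and after each iTBS day".

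**What the safety endpoint uses.** Primary Safety Endpoints and Associated Stop Rules (IV.C.i item 2, repeated in IX.C.i) says that only Trails B "will be evaluated in relation to this stop rule". The criterion is "A completion time for Trails B greater than 90 seconds", applied to the time after iTBS. A participant above it rests for 60 minutes and is retested. A second time above the same cut-off calls for evaluation by the medical investigator or covering clinician. Discharge and unblinding follow only if that clinician judges that outside evaluation or treatment is needed.

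**Study-level hold.** "If more than 1 neurocognitive event identified with Trails B is seen within any 10 consecutive participants", iTBS is paused for review by the PI, FDA and DSMB.

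**Between-arm analysis.** "Chi-square tests will be calculated to test frequency differences between groups (active iTBS vs sham iTBS) for each of these endpoint measures".

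Statistical Analysis (III.G.vi) plans repeated-measures ANOVA and linear mixed models for cognitive-task performance and questionnaires. It does not name Trails B.

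**The concern.** The design measures each participant's own reference value, both that morning and before any stimulation. The endpoint that should show whether iTBS impairs cognition does not refer to it. Two consequences follow.

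First, slowing that ends at or below 90 s adds nothing to the between-arm comparison, however large it was for that person. Second, a participant who was above 90 s before stimulation and stays there enters the chain in the same way as one whom iTBS pushed over the line. The count alone cannot tell them apart.

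Monitoring safety in cocaine-dependent participants is Aim 5 (III.C), and this is one of three primary safety endpoints. The text also does not say whether a neurocognitive event is the first time above 90 s, the confirmed repeat or the clinician's referral. Both the chi-square and the hold depend on that choice.

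**Working it through.** The plan gives no event rate, power or Trails B distribution for this endpoint, so it has no figure of its own to reproduce. The check has a text part and an illustration.

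**1. Logic of the rule (no assumptions).** The first trigger is post-iTBS time above 90 s.

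| Pre (s) | Post (s) | Change (s) | Triggers? |
|---|---|---|---|
| 40 | 85 | +45 | no |
| 60 | 89 | +29 | no |
| 95 | 95 | 0 | yes |
| 100 | 91 | −9 | yes |

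No listed eligibility criterion limits baseline Trails B. By contrast, the cocaine-use rule (IV.C.ii) is set against the participant's own greatest previous binge.

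**2. Power of the two comparisons (assumed inputs).** From the documents: 45 per arm, 10 iTBS days, the 90 s cut-off and the repeat. Assumed: normal times with mean 65 s, between-person SD 18 s and within-person SD 8 s; two-sided 5% level; an event is a post-iTBS time and a repeat both above 90 s on any day. The background event rate is then about 14% per participant.

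Simulated power:

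| Uniform slowing | Chi-square | Adjusted for pre-iTBS time |
|---|---|---|
| 3 s | 0.08 | 0.98 |
| 6 s | 0.19 | about 1.0 |
| 15 s | 0.81 | about 1.0 |

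Closed-form check of the adjusted column. A 10-day mean has error SD 8/√10 = 2.53 s. Post given pre has SD of about 2.53 × √2 = 3.58 s. SE = 3.58 × √(2/45) = 0.754 s. Power at 3 s = Φ(3/0.754 − 1.96) = Φ(2.02) = 0.98, in agreement.

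**3. Less favourable assumptions for the adjusted comparison, 3 s slowing.**

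- 30 per arm (the completer target) and 5 days (the minimum for entry to follow-up): SD = (8/√5) × √2 = 5.06 s; SE = 5.06 × √(2/30) = 1.31 s; power = Φ(2.30 − 1.96), about 0.6.
- Change varying between people with SD 10 s, 45 per arm, 10 days: SD = √(3.58² + 10²) = 10.6 s; SE = 10.6 × √(2/45) = 2.24 s; power = Φ(1.34 − 1.96), about 0.3. At 6 s it is Φ(2.68 − 1.96), about 0.76.

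**4. A different assumed model.** One day, mean 60–90 s, SD 20–30 s, pre/post correlation 0.6–0.8, 15 s slowing, 45 per arm: chi-square power is 39–78%, against 84% to above 99% adjusted. With 30 per arm it is 28–60% against 68% to above 99%. With no iTBS effect, 34–80% of post-iTBS times above 90 s come from people already above 90 s beforehand.

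**5. The hold under different event rates.** In one block of 10, P(at least 2) = 1 − (1−p)^10 − 10p(1−p)^9, which is 8.6% at p = 5% and 26% at p = 10%. For any run of 10 among 90 participants with no iTBS effect, simulation gives:

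| Event rate per participant | Chance of a hold |
|---|---|
| 0.5–1% | about 2–7% |
| 2% | 22% |
| 5% | 71% |
| 10% | 98% |

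The answer turns almost wholly on which step of the chain is counted.

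**The case against.** The strongest case is that this is a screen for acute impairment, not an estimate of mean change. Nothing in the documents makes a 3–6 s mean shift a safety concern, and the chi-square performs reasonably against large effects. That stands. A reader might infer that real slowing would usually go undetected; the 15 s figures do not support so general a statement.

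A reader might also infer that the rule rests on a single slow time. It does not. The 60-minute repeat and clinician evaluation soften the consequence for a habitually slow person, and if only referrals count, such a person may never be counted. But the repeat uses the same 90 s, no text directs the clinician to the pre-iTBS value, and neither step can recover slowing that ends at or below 90 s.

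Randomisation balances slow participants between arms on average, so the documents do not support calling the chi-square biased; the loss is of sensitivity. The pooled hold has no such protection. However, a hold is a pause for review while contingency management, scans and follow-up continue, and leaning towards pausing can be deliberate. Because the event is undefined, frequent false holds cannot be asserted either. Exclusion of cognitive impairment at entry (III.F.ii criterion 6) also limits habitual slowness to some degree.

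Finally, the mixed models in III.G.vi might be extended to Trails B, so it goes too far to say the pre-iTBS times are discarded. But Trails B is not named there, and IV.C.i assigns this endpoint to chi-square.

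**Conclusion.** The point holds in a limited form. As stated, the trigger, the repeat, the hold and the between-arm test all leave out the same-day pre-iTBS time and the baseline collected "to assess a true baseline measure for each participant". The comparison is consequently insensitive to modest slowing, and its counts cannot separate prior slowness from slowing by iTBS. The text findings need no assumption.

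The size is illustrative only. The gain from adjustment is large for modest uniform slowing and smaller when slowing is great. With fewer participants and days, or when the effect varies between people, the adjusted analysis itself has limited power at 3 s. The undefined event is mainly a matter of clarification, but it decides what both the chi-square and the hold count. The documents do not require that the prespecified count above 90 s be reduced to a descriptive result; that would be a preference.

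**What to change.** 1. Keep the chi-square on the count above 90 s. Add a between-arm linear mixed model of post-iTBS Trails B time (log scale) in the randomised CD participants, with arm, iTBS day and same-day pre-iTBS time as fixed effects and a random participant effect. Report the arm effect with its confidence interval.
2. Tabulate the count above 90 s by arm and by whether the same-day pre-iTBS time was already above 90 s.
3. Ask the sponsor and DSMB to state whether a neurocognitive event is the first time, the repeat or the clinician referral, for both the chi-square and the hold, and to reconcile that with the pre/post design in IV.C.i and IX.C.i. No threshold or clinical rule is proposed here.

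The cost is one extra model and one table on data already collected, plus a clarification of the monitoring text. No visits or assessments are added.
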